## X. Potential risks and benefits to subjects

### Potential Risks

A potential risk of this intervention is vitamin D-mediated hypercalcemia. Given the exclusion criteria which screens for those at increased risk for developing hypercalcemia, this risk is anticipated to be low and will be monitored for throughout the intervention period via quarterly lab draws regularly reviewed by investigators, the DSMB, and the Clinical Advisory Committee. In addition, high doses of vitamin D have been associated with an increased risk of falls. Our exclusion criteria also attempts to minimize the likelihood of this risk by screening for those before enrollment at increased risk for developing this side effect. This risk will also be monitored in subject self-reports during survey administration. We believe this risk to be low in this study population. As with any study that involves blood draws, participants will also be exposed to the minimal risks of phlebotomy including pain, infection, and venous damage. These risks will be mitigated by using professionally trained phlebotomists. Since protected health information (PHI) is collected on web-based software, there is also a risk to loss of confidentiality, which we believe to be minimal. Precautions to minimize these risks are detailed below.

### Protections Against Potential Risks

The risks as described in "Potential Risks" we believe to be unlikely and will be mitigated whenever possible. The nature of the intervention and all risks will be fully described to subjects, moreover, subjects will be informed that they can choose to discontinue and withdraw from the study at any time. Subjects can also choose to not answer any question on the survey. For the risk of loss to confidentiality, all members of the study team will maintain strict standards for confidentiality, further described in Section XIV and thus not repeated here. The risk of complications due to venipuncture will be mitigated by use of trained professional phlebotomists at UCM and RU. The risks of complications due to higher doses of vitamin D will be mitigated with the exclusion criteria as outlined above during preliminary screening and through subject education of symptoms for fall risk. Vitamin D-mediated hypercalcemia will be mitigated by regular monitoring by investigators for critical calcium values during blood draws and subject education of symptoms related to hypercalcemia. Subjects at UCM will be referred to their primary care provider if they experience these symptoms or have calcium levels of 10.5-12 mg/dL and subjects at Rush will be referred to their primary care provider if they experience these symptoms or have calcium levels of 11.3-12mg/dL. For all subjects, if calcium laboratory values are 12.1mg/dL-14mg/dL, subjects will be advised to go to urgent care and if values are greater than 14 mg/dL subjects will be advised to seek care at an emergency room. Subjects will be provided with the pager number of an on-call physician at UCM and Rush primary care group that they can use in the event of emergent symptoms.

### Potential Benefits

Health care workers (HCWs) and those who reside in diverse metropolitan communities with high community spread of COVID-19 are of special public health relevance because of their 1) increased exposure to COVID-19, 2) frequent contacts with individuals at increased risk of infection and adverse outcomes if infected, and 3) frequent contact with others who could spread COVID-19. We intentionally do not seek a representative sample because our primary goal is to learn if vitamin D treatment is efficacious in reducing COVID-19 incidence and improving outcomes and the higher risk populations we will focus on facilitates that. We think that if we find evidence of effectiveness among our study population, the low risks and costs of vitamin D treatment would encourage widespread use of vitamin D more broadly, producing health benefits throughout the population. Nevertheless, even if one thought the results could only be generalized to HCWs and those in metropolitan communities, the public health impact of this work would be significant for the reasons above.

## XI. Monitoring of safety

The current study represents a multi-site clinical trial in which the risks inherent to the intervention are of minimal risk to participants given the long-standing use of vitamin D supplementation with few adverse events. The protocol's exclusion criteria and monitoring plan limit the likelihood that subjects will develop a severe medical condition during the course of this study. Commensurate with these risks, the PI [name], with support from the Clinical Advisory Committee and co-investigators Drs. [name], [name], [name], and [name], will conduct regularly monitoring of safety which will be overseen by a formal Data and Safety Monitoring Board (DSMB). The independent DSMB will be comprised of three experts, a Chair and two members, who will provide regular oversight for this multi-site study. The PI has already identified all three DSMB members, one of whom will be the Chair. These individuals are senior faculty members and hold expertise in clinical trial oversight and design, biostatistics, endocrinology, pulmonology and critical care medicine.

The protocol's safety and monitoring guidelines as described below have been created in collaboration with the already-identified members of the Clinical Advisory Committee, a committee of interdisciplinary clinicians who will provide the PI clinical support and guidance. If funded, the protocol will be overseen by the DSMB which will provide continued guidance on administration of the study protocol and management of any adverse events. The DSMB will work closely with the PI, co-investigators, and Clinical Advisory Committee, monitoring the intervention on an ongoing basis and meeting quarterly to review intervention data and provide recommendations as needed for modifying the intervention. Study analysts will work with the PI and Co-Investigators to send laboratory data to the DSMB regularly for review.

### [Ensuring subject safety](#)

[figure not shown]
The proposed study will be supervised by PI and the Clinical Advisory Committee, with oversight by the DSMB and the University of Chicago Biological Sciences Division Institutional Review Board (UCM BSD IRB). All subjects will undergo written informed consent. Additional safety precautions include: 1) exclusion of individuals for whom higher dose vitamin D supplementation is more likely to be unsafe, 2) written materials on possible side effects of vitamin D supplementation provided at consent (i.e., risk of falls, symptoms of hypercalcemia), 3) monitoring of calcium levels to detect toxicity, 4) participants will be advised to report adverse events (email and study phone number provided), 5) independent testing of vitamin D supplements to ensure accurate potency, 6) rigorous infection control practices to mitigate the spread of COVID-19 at UChicago Medicine where testing is performed and 7) well-trained research staff.

### [Monitoring of the intervention](#)

To monitor for toxicity, calcium levels will be checked at study initiation to assess for baseline hypercalcemia and at each subsequent blood draw (3, 6, and 9 months) to monitor for incidental or study-induced hypercalcemia. If study participants are found to be hypercalcemic, they will be told to cease vitamin D supplementation. For UCM patients with a calcium level 10.5-12 mg/dL and for Rush patients with a calcium level of 11.3-12mg/dL, patients will be instructed to consult with their primary care physician. For patients with a calcium level of 12.1-14 mg/dL, patients will be referred to urgent care. For patients with a calcium level greater than 14 mg/dL, patients will be referred to the emergency room. These participants will continue to undergo monitoring blood draws and surveys and may resume vitamin D supplementation per study protocol with a physician note. Based on conversations with our Clinical Advisory Board and prior studies, we expect very few people to become hypercalcemic due to study medication. The DSMB will also conduct an interim analysis of COVID-19 incidence among the two study arms approximately 6 months into the study to determine study continuation in addition to routine safety review.

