### Procedures and Materials

Blood labs will be taken from subjects at intake, 3 months, 6 months and, if in the 9-month cohort, 9 months. If subjects are in the 2023 cohort (defined as recruited on or after January 1, 2023) blood labs will be taken from

subjects at intake, 3 months, and, if they are recruited in January or February 2023, they will have one final blood draw in June 2023. Labs for UCM subjects will be drawn at DCAM phlebotomy, River East phlebotomy, or Ingalls Hospital, depending on the location most convenient for the subject. Labs for Rush subjects will be drawn by [name] at his Rush lab.

Intake labs will measure baseline calcium and PTH levels, presence of COVID-19 antibodies, baseline vitamin D levels, and vitamin A levels. Where possible given constraints related to sample storage, analysis and available funding for free vitamin D measurement, vitamin D measurements will include free vitamin D levels measured by ELISA assay, as well as total vitamin D levels.

For Aim 7, Intake labs for UCM subjects will additionally measure vitamin D-binding protein (DBP), RAS components (Renin, Ang II, soluble ACE and ACE2), bradykinin, inflammation markers (IL-6, TNF- $\alpha$ , IL-1 $\beta$  and CRP), and SARS-CoV-2 antibodies against S-protein and N-protein.

Follow-up labs (excluding the final lab) will measure PTH levels, calcium levels, vitamin A levels for those who have high baseline vitamin A, and vitamin D levels for monitoring of the intervention's safety and outcomes, and COVID-19 antibodies for monitoring of the outcome. Records of these levels will be kept by the UCM and RU PIs and laboratories.

Final labs will measure calcium levels, vitamin D levels for monitoring of the intervention's safety and outcomes, and COVID-19 antibodies for monitoring of the outcome. Records of these levels will be kept by the UCM and RU PIs and laboratories. Final labs will not measure PTH levels. During the intervention period, our study monitors PTH levels for active participants, because primary hyperparathyroidism is a risk factor for vitamin D toxicity. Given that participants will no longer be taking study-provided vitamin D after their final lab draw, we do not believe it is medically necessary or an appropriate use of limited study resources to continue checking PTH levels with this final draw.

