Those who enroll in March 2023 will have baseline labs in March 2023 and final labs in June 2023 (3 months later). This is due to the end of study funding in June 2023. This is further specified in Section IV, Table 4 below.

Testing for calcium, PTH, and vitamin D will be done at UCM (UCMC, River East, or Ingalls) or Rush ([name]'s lab), with the site for each subject selected based on which site is most convenient for the subject. Vitamin A, which will be drawn only from UCM subjects, will be sent to an outside lab for analysis. Throughout the study period we will tell subjects about calcium, PTH and vitamin D lab results only if they suggest a safety concern for which we would like them to seek care from a medical professional. Except in the instance of a safety concern, subjects will be blinded to their vitamin A & D levels, calcium and PTH throughout the study to ensure protocol compliance. At the end of their time in the study, we will provide test results to subjects as indicated in "Study Completion Email V4". At the end of the intervention period for all participants in this protocol, we will unblind participants to their vitamin D dose assignment as indicated in "Dose Unblinding Email V1". We will do this at the end of the intervention for all participants because we, as the study team, are also currently blinded to dose assignments until the end of the intervention period for all participants. For participants who transition to participate in protocol 20-0847, unblinding will occur at the end of the intervention period for all participants in that study. Blood draws for COVID-19 antibodies will also occur at same location as their other lab draws for convenience, consolidated with other labs, but antibody testing will occur at UCM using the Roche assay for consistency given the differing ranges of different COVID-19 assays. Subjects will be instructed during the consent process to seek COVID-19 PCR testing on their own at a site convenient for them if they become symptomatic or were exposed to COVID-19, which is aligned with recommendations from CDC and IDPH. COVID-19 PCR tests will not be part of the research labs, and thus will not be paid for by the study. Subjects will self-report positive COVID-19 PCR results in the quarterly survey. Laboratory records will be monitored regularly by site PIs, Co-Investigators, and members of the DSMB and Clinical Advisory Committee for safety. Patient-reported outcome measures will be measured by a RedCap-based survey.

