**Table 3: Subject timeline in study: For subjects recruited after March 31, 2022 and before January 1, 2023**

Date	Activity	Description
Baseline (Month 0)	Recruitment and enrollment	
 
Subjects will be screened for eligibility, undergo initial blood draws, and undergo randomization.
 

		
 
Subjects will be given 9-month supply of vitamin D with instructions for daily intake. Subjects will complete the intake survey via telephone or web.
 

Month 3	Wave 1	
 
Subjects will visit the lab for their follow-up Wave 1 blood draws. CRCs will call or email subjects to remind them of the lab visit as needed until the lab visit is confirmed completed.
 
Subjects will also be sent the first follow-up web-based survey via email or text message. CRCs will call and email subjects as needed to remind them to complete the survey.
 

Month 6	Wave 2	
 
Subjects will visit the lab for their follow-up Wave 2 blood draws. CRCs will call or email subjects to remind them of the lab visit as needed until the lab visit is confirmed completed.
 
Subjects will be sent the second follow-up web-based survey. CRCs will call and email subjects as needed to remind them to complete the survey. For the 6-month subject cohort, this set of labs will be their final set of labs and surveys.
 

Month 9	Wave 3	
 
Subjects in the 9-month cohort (those recruited before October 1, 2022) will visit the lab for their final blood draws in this wave. CRCs will call or email subjects to remind them of the lab visit as needed until the lab visit is confirmed completed.
 
Subjects will also be sent the final follow-up web-based survey. CRCs will call or text subjects to remind them to complete the survey.
 

Months 10-23	Final analysis & chart review	
 
Final analyses and reporting of the intervention effects on outcome measures will take place during this period to prepare for dissemination.
 
Chart review evaluating outcomes (e.g., hospitalization, positive COVID test)
 
For both the 6-month and 9-month cohorts, chart review will occur for 12 months after their participation
 

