**Table 4: Subject Timeline in Study: For subjects recruited in the study on or after January 1, 2023 but before March 31, 2023 (end of recruitment period)**

Date	Activity	Description
Baseline (Month 0)	Recruitment and enrollment	
 
Subjects will be screened for eligibility, undergo initial blood draws, and undergo randomization.
 
Subjects will be given a bottle of vitamin D with instructions for daily intake. Subjects will complete the intake survey via telephone or web.
 

Month 3	Wave 1	
 
Subjects will visit the lab for their follow-up Wave 1 blood draws. CRCs will call or email subjects to remind them of the lab visit as needed until the lab visit is confirmed completed.
 

		
 
Subjects will also be sent the first follow-up web-based survey via email or text message. CRCs will call and email subjects as needed to remind them to complete the survey.
 
For subjects recruited March 1-31, 2023, this will be their final blood draw and survey
 

Final month (June 1-30, 2023)	Wave 2	
 
This second round of follow-up labs will apply to those recruited in January and February 2023
 
Subjects will visit the lab for final blood draws. CRCs will call or email subjects to remind them of the lab visit as needed until the lab visit is confirmed completed.
 
Subjects will be sent the second follow-up web-based survey. CRCs will call and email subjects as needed to remind them to complete the survey. For the 6-month subject cohort, this set of labs will be their final set of labs and surveys.
 

Months 4-18	Final analysis & chart review	
 
Final analyses and reporting of the intervention effects on outcome measures will take place during this period to prepare for dissemination.
 
Chart review evaluating outcomes (e.g., hospitalization, positive COVID test)
 
Chart review will occur for 12 months after this cohort's participation
 

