## VI. Special precautions, including dose modifications

We will not make modifications of the vitamin D dose based on the study design. As described in Section XI, "Monitoring Subject Safety", subjects will be advised to cease vitamin D supplementation if specific lab values

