8. Report already taking more than 400 IU of vitamin D daily as recommended by their health care provider, excluding multivitamins and excluding supplements that include vitamin D and calcium together, unless permission is received from the prescribing health care provider to participate. In this case, no more than 1,000 IU vitamin D may be taken daily in addition to the study medication and we would limit the subjects to participation in the low vs. moderate arm of the study, producing a maximum dose of 5,000 IU per day. We note that the NAM recommended a maximum dose of 4,000 IU per day without medical supervision based on evidence that 5,000 was safe and known uncertainty about the precision of dosing in 5,000 IU supplements available over the counter. However, since we are testing the dosage of our 4,000 IU supplements to high precision and these patients would be taking their original supplements with a labelled dose of 1,000 IU or less, we think that the combination of our 4,000 IU supplements and the patient's original supplement of up to 1,000 IU should not provide a maximum dose meaningfully above the 5,000 IU actual dose the NAM has considered safe for taking without medical supervision. We note further that we are measuring vitamin D levels and PTH in these patients regardless in this study. We do, however, have another study of vitamin D and COVID (IRB# 20-0847), in which we are not measuring these levels, for which it is more important to not substantially exceed NAM maximum level of 5,000 IU per day. The approach described here allows us to align the approach in these two studies.
9. Report taking D2.
10. Report a history of sarcoidosis.

11. Screen positive for hypercalcemia ( at UCM, defined as >10.4 mg/dL and at Rush, defined as >11.2 mg/dL) during the initial blood test.
12. Screen positive for hyperparathyroidism (PTH>85 pg/dL) during the initial blood test with calcium  $\geq 10$ mg/dL and normal levels of vitamin D ( $\geq 30$ ng/mL)
13. Have vitamin D levels of >100ng/mL at study start, or >250ng/mL during follow-up labs.
14. Are unwilling to provide blood samples during quarterly blood tests.
15. Are unwilling to take daily vitamin D.

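### After a stop for hypercalcemia, the readable restart rule asks for a physician note but no calcium value, and adds no study calcium before the next scheduled draw

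*Combined protocol and SAP*

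**What the plan says.** **Stop and referral.** Section XI, Monitoring of the intervention, tells a hypercalcemic participant to stop. It then refers by band: primary care from 10.5 (UCM) or 11.3 (Rush) to 12 mg/dL, urgent care for 12.1 to 14, and the emergency room above 14.

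**Restart.** One sentence follows the three bands. These participants stay on the monitoring draws and surveys and "may resume vitamin D supplementation per study protocol with a physician note". Section XIV repeats this in its account of what participants are told about hypercalcemia, so it is not limited to the highest band.

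**Dose.** Section VI: "We will not make modifications of the vitamin D dose based on the study design".

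**Calcium schedule.** Calcium is measured at initiation and "at each subsequent blood draw (3, 6, and 9 months) to monitor for incidental or study-induced hypercalcemia". Shorter cohorts have fewer draws. Table 3 says of month 6: "For the 6-month subject cohort, this set of labs will be their final set of labs and surveys". Table 4 says of month 3: "For subjects recruited March 1-31, 2023, this will be their final blood draw and survey".

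**End of dosing.** Section III, Procedures and Materials: "participants will no longer be taking study-provided vitamin D after their final lab draw".

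**The concern.** Hypercalcemia is the main toxicity the plan monitors for. A participant who has already shown it is a person in whom a repeat is plausible, yet the readable rule does not ask whether calcium has come down before the same dose is restarted. It also does not bring the next study measurement forward.

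At stake is individual safety, not the efficacy comparison. On the text as readable, a participant could restart up to 10,000 IU/day while calcium is still above the site limit, and the study itself might not measure calcium again for up to about three months.

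**Working it through.** The plan gives no figure to reproduce here. The check is a comparison of rules, followed by a count of days from the visit schedule.

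**1. The restart rule beside the plan's own rules**

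| Situation | Calcium condition | Extra study calcium |
|---|---|---|
| Entry (Section VIII, exclusion 11) | Excluded if hypercalcemic: "at UCM, defined as >10.4 mg/dL and at Rush, defined as >11.2 mg/dL" | Not applicable |
| Reported history of hypercalcemia (exclusion 5) | Excluded outright | Not applicable |
| Starter with raised PTH, low vitamin D and calcium below 10 mg/dL (Section III, Summary) | Calcium must be below 10 mg/dL | Yes, 30 days after starting |
| Restart after on-study hypercalcemia, any band (Sections XI and XIV) | None stated; physician note | None stated |

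The plan is therefore stricter with a new entrant, and with a starter whose calcium is normal, than with a participant whose calcium has already gone above the limit on study drug.

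**2. Which draw comes next**

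Restart matters only after a draw that still has dosing ahead of it.

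| Cohort | Draw showing hypercalcemia | Next scheduled calcium | Is it the final draw? |
|---|---|---|---|
| 9-month | Month 3 | Month 6, about 91 days later | No |
| 9-month | Month 6 | Month 9, about 91 days later | Yes |
| 6-month | Month 3 | Month 6, about 91 days later | Yes |
| January-February recruits (Tables 2 and 4) | Month 3 | June | Yes |
| March recruits | Month 3 is itself final | None | Not applicable |

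For January-February recruits in 2023 (Table 4; Table 2 has the same pattern for 2022):
- Recruited January 1: month-3 draw April 1; June 1 to 30 is 61 to 90 days later.
- Recruited February 28: month-3 draw May 28; June 1 to 30 is 4 to 33 days later.
- The range is about 4 to 90 days.

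Where the next draw is final, its result cannot shorten the restarted course, because study drug ends with it. Raised-PTH starters have one additional early calcium, at 30 days; an abnormal value there is followed by month 3, about 91 − 30 = 61 days later.

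**3. Time on restarted drug before the next study calcium**

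Inputs: draws about 91 days apart (three months). Assumption, not in the documents: restart 7 to 30 days after the stop, with the stop taken as the day of the draw.

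- Current text: 91 − 30 = 61 days, to 91 − 7 = 84 days.
- With a recheck at about 30 days: 61 − 30 = 31, to 84 − 30 = 54 days sooner.
- Outer bound, restart on the day of the draw: 91 days against 30. At 10,000 IU/day that is 910,000 IU against 300,000 IU taken before a study calcium; at 4,000 IU/day, 364,000 IU against 120,000 IU.

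**The case against.** The strongest objection is that the absence lies where the documents cannot be read. The UCM, Rush and PTH referral algorithms are figures that are not shown, and Section VI breaks off while describing when participants are told to stop. A retest step could sit in any of these. This stands: the point is about the readable text only, and a reader should not infer that the whole plan lacks a retest.

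Second, restart is not automatic. The participant has been stopped and sent to graded care, and a physician must clear restart in writing. Many physicians would repeat calcium first. This also stands as a matter of likelihood, but the readable text neither requires the value nor has the study record it.

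Third, other routes to stopping exist:
- Section III (Summary) treats hypercalcemia as an adverse event calling for a stop and evaluation.
- Section X provides referral on symptoms and an on-call pager.
- Section XI provides symptom materials, adverse event reporting by participants and ongoing DSMB oversight.
- Section XII sends adverse events to the DSMB at once and has it review laboratory trends.

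These are real protections. None of them sets a calcium value for restart or schedules a draw.

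Fourth, the 30-day interval is borrowed from first-time starters with possible primary hyperparathyroidism, a different group. That is fair. It is offered as an interval the trial already operates, not as a derived optimum.

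**Conclusion.** The point holds as a modest, inexpensive safety improvement. In the readable text, a participant stopped for hypercalcemia in any band may resume the unmodified dose on a physician note, with no stated calcium value and no study calcium before the next scheduled draw. That draw is at most about 3 months away, or 61 to 84 days under the assumed restart delay where draws are 91 days apart. It is the final draw after month 6 in the 9-month cohort and after month 3 in the shorter cohorts. Section XI expects very few hypercalcemia cases due to study drug and gives no number, so the count affected is unknown and probably small.

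Two stronger readings are tempting and not supported:

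- A reader might infer from the schedule that most restarts would be followed only by the final draw, since this is so in three of the four positions in the second table. Those are positions, not participants. No cohort sizes are given, within the 9-month cohort it is one of two, and early-2022 recruits could re-consent to nine months (Section XIV).
- A reader might infer that the physician must decide without useful information because the dose is masked (Section III: "we, as the study team, are also currently blinded to dose assignments until the end of the intervention period for all participants"). But the same section releases calcium, PTH and vitamin D results when they raise a safety concern, and vitamin D is measured at follow-up draws. A clinician can therefore have direct evidence on toxicity without knowing the assignment.

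**What to change.** In Section XI (Monitoring of the intervention), and in the matching account in Section XIV and the consent form, replace the restart condition with:

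> Study drug may resume only with a physician note and a documented calcium, taken after the stop, at or below the site limit (10.4 mg/dL at UCM, 11.2 mg/dL at Rush). Calcium is rechecked about 30 days after restart, or at the final draw if that comes first, and the same stop and referral steps apply to that value.

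The limits are those of exclusion 11 and the interval is the one already used for raised-PTH starters. For late recruits with only days to the June draw, the recheck merges with the final draw. If the referral figures already require these steps, practice need not change; the text sections should then simply say the same.

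The cost is two sentences in an amendment and the consent wording, one extra calcium per restart, and possibly one pre-restart value if the treating physician has not taken it. No unblinding is needed. The downside is that a very small number of participants restart later or not at all, with slightly delayed or lost exposure.
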